6.3 Physical Examination

A complete physical examination will be performed by the Investigator at Screening. At the time points specified in Table 1, subsequent directed physical examinations will be performed according to standard institutional practices and must be documented in source documents.

Body weight and height will be measured at Screening only.

6.4 Vital Signs

Vital signs (heart rate [HR] and blood pressure [BP]) will be recorded at time points specified in Table 1. Blood pressure and HR will be assessed according to standard practice at the clinical sites. Study personnel will record vital sign measurements in the eCRF.

Vital signs measurements are to be repeated if clinically significant changes or machine errors occur. Out of range BP and HR will be repeated at the Investigator's discretion. Semi-supine BP and HR will be measured more frequently if warranted by the clinical condition of the patient.

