6.5 Twelve-Lead Electrocardiogram

Triplet 12-lead electrocardiograms (ECGs) will be performed within a 5-minute interval at the time points outlined in Table 1.

The patient should be stabilized in a supine position for 5 minutes before recording the ECG at Screening. The ECG recordings should allow a full assessment of QT intervals. Machine-read values for QTc/QTcF will be evaluated for determination of eligibility at Screening. If the quality of the ECG is insufficient then it must be repeated. All ECG data must be reviewed by the attending physician and any findings of clinical significance found following Screening will be recorded as AEs in the eCRF. In addition, advice may be sought from appropriate cardiologists, if necessary. All ECGs will be made available to the Sponsor for review and might be sent to a Cardiac Core Laboratory for further evaluation.

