6.6 Clinical Laboratory Tests

Safety laboratory tests will be performed at the time points specified in Table 1 and sent to a local laboratory. Additional tests may be performed at the discretion of the Investigator if deemed clinically appropriate. If required, samples may be sent to a central laboratory for confirmation of local results.

A full list of the clinical laboratory tests that will be performed and analyzed is presented in Section 21.1.

Any safety laboratory results outside the normal range will be repeated at the discretion of the Investigator and will be evaluated by the Investigator or designee as "clinically significant (CS)" or "not clinically significant (NCS)." Any CS value should be repeated as necessary and followed until resolution.

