9.6 Safety Analysis

Safety will be evaluated in the Safety Analysis Set by presenting summaries of AEs and vital signs.

Summary tables will be provided for all TEAEs. A treatment-emergent AE is defined as an AE with a start date and time on or after the first dose of study drug. Adverse events will be coded using the Medical Dictionary for Regulatory Activities (MedDRA®). The number and percentage of patients with TEAEs will be tabulated by system organ class and MedDRA Preferred Term for each treatment group and by severity and relationship to treatment.

Adverse events leading to premature discontinuation from the study drug and serious TEAEs will be presented either in a table or a listing.

Descriptive statistics of vital signs and the change from baseline for each scheduled evaluation will be summarized at each study visit and the worst overall post-baseline value will be provided. The number and percent of patients with treatment-emergent values with potential clinical significance will be tabulated.

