21.2 Appendix 2: Values of Potential Clinical Concern

Haematology

Hemoglobin Males: < 12.0 or > 18.0 g/dl Females: < 10.5 or 16.1 g/dl

Hematocrit Males < 36.0 or > 54.0% Females: < 31.0 or > 50.6%

Leukocytes > 1 K/ μ l below or > 3 K/ μ l above the limit of the reference range

Platelets < 80 or > 500 K/ μ l

Chemistry

Total bilirubin \geq 1.5 times upper limit of the reference range

AST > 2 times upper limit of the reference range

ALT > 2 times upper limit of the reference range

GGT > 2 times upper limit of the reference range

Alk Phosphatase > 1.5 times upper limit of the reference range

Creatinine > 1.8 mg/dl

BUN > 1.5 times upper limit of the reference range

Glucose, fasting < 60 or > 126 mg/dl

Uric acid > 11 mg/dl

Sodium > 5 mEq/l above or below the limits of the reference range

Potassium > 0.5 mEq/l above or below the limits of the reference range

Calcium < 7.2 or > 12 mg/dl

Phosphate > 0.8 mg/dl below or 1.0 mg/dl above the limits of the reference range

Albumin > 0.5 g/dl above or below the limits of the reference range

Total protein > 1.0 g/dl above or below the limits of the reference range

Urinalysis

WBC > 15/hpf

RBC > 15/hpf

Vital Signs

Heart Rate Supine: < 35 or > 120 bpm Erect: < 40 or > 140 bpm

Blood Pressure Systolic > 30 mmHg change from baseline in same posture

Diastolic > 20 mmHg change from baseline in same posture

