21.3 Appendix 3: ECG Values of Potential Clinical Concern

Electrocardiogram

PR interval < 120 ms; \geq 220 ms

QRS interval \geq 120 ms

QTc interval(Bazett's)

> 470 ms (adult females \leq 50 yrs old)

> 480 ms (adult females $>$ 50 yrs old)

> 470 ms (adult males)

Rhythms of Potential Clinical Concern

-Asymptomatic Marked Sinus Bradycardia (rate < 35 bpm)

-Asymptomatic Supraventricular Couplets, Atrial Bigeminy lasting > 30 seconds

-Asymptomatic Ventricular Couplets, Ventricular Bigeminy lasting > 30 seconds

-Asymptomatic Type I Second Degree (Wenckebach) AV Block of > 30 seconds duration

-Asymptomatic Frequent Premature Ventricular Complexes (PVCs) (\geq 144/24 hours)

-Asymptomatic Frequent Premature Atrial Complexes (PACs) (\geq 240/24 hours)

Adverse Experiences

-Symptomatic Marked Sinus Bradycardia (rate < 40 bpm)

-Asymptomatic Sinus Pause > 3 seconds without an escape beat

-Asymptomatic Atrial Flutter or Fibrillation, subcategorized by ventricular response rate:
controlled = rate < 120 bpm; rapid = rate \geq 120 bpm

-Asymptomatic Supraventricular Tachycardia \geq 3 beats (rate \geq 120 bpm)

-Asymptomatic Nonsustained Ventricular Rhythms \geq 3 beats, but duration of < 30 seconds, including idioventricular rhythm (rate < 40 bpm), accelerated idioventricular rhythm ($40 \leq x < 100$) and monomorphic/polymorphic ventricular tachycardia \geq 100 bpm (such as Torsade des pointes)

-Asymptomatic Type II Second Degree (Mobitz) AV Block

-Asymptomatic Complete (third degree) Heart Block

Serious Adverse Experiences

-Sustained Ventricular Arrhythmias (> 30 seconds duration)

-Ventricular Fibrillation

-At the discretion of the investigator, any arrhythmia classified as an adverse experience

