8.2 Clinical laboratory evaluation

Statistical analysis

Hematology, biochemistry parameters and their change from screening will be summarised by cohort at each available visit by means of descriptive statistics.

Shift tables presenting the number and the percentage of patients in each bivariate category (screening visit versus Visit 9) with regards to Investigator’s interpretation (Normal, NCS, CS) will be presented by cohort for all laboratory parameters.

Urinalysis parameters will be listed only.

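### The SAP never applies the protocol's numeric limits of concern, omits the promised vital-signs count without saying so, and posture and QT correction are left unspecified

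*Protocol*

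**What the plan says.** **Limits.** Protocol Appendix 2 gives heart-rate limits by posture: "Heart Rate Supine: < 35 or > 120 bpm Erect: < 40 or > 140 bpm". Its blood-pressure limits are changes from baseline of more than 30 mmHg systolic or 20 mmHg diastolic, both readings in one posture. It also holds numeric limits for haematology, chemistry and urine. Appendix 3 gives PR, QRS and QT limits, the last under a label that begins "QTc interval(Bazett's", and some rhythm limits expressed as counts per 24 hours.

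**Collection.** On vital signs, Protocol 6.4 says "Blood pressure and HR will be assessed according to standard practice at the clinical sites". The only posture it names is for additional readings: "Semi-supine BP and HR will be measured more frequently if warranted by the clinical condition of the patient". Protocol 6.5 schedules triplicate 12-lead ECGs, which Table 1 places at Screening and Day 28, and adds: "Machine-read values for QTc/QTcF will be evaluated for determination of eligibility at Screening". For laboratory results, Protocol 6.6 has the investigator or a designee call out-of-range values clinically significant or not.

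**Analysis.** Protocol 9.6 says of vital signs: "The number and percent of patients with treatment-emergent values with potential clinical significance will be tabulated". The synopsis makes the same commitment. SAP 8.3 plans descriptive statistics and change from baseline by cohort and visit, and Table 14.3.3.1 is the only vital-signs table. SAP 8.2 summarises haematology and biochemistry values and their change from Screening, and adds shift tables on the investigator's Normal/NCS/CS interpretation. SAP 8.4 lists ECG data only, with QTc and QTcF as separate items. SAP 4.8 sets out the changes from the protocol's analyses; none concerns vital signs, laboratory values or ECGs.

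**The concern.** Safety is the primary objective, and the protocol fixes in advance which values deserve attention. If the analysis never uses those limits, the choice of which abnormal values to highlight is left until the data have been seen, or to a label given by an investigator who knows the dose.

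The vital-signs part matters most, because there a promised analysis has disappeared without being declared. Restoring it is not simply a matter of programming: the limits depend on posture, and the protocol neither fixes posture nor requires it to be recorded. SAP 3.1 refers to protocols in five countries, so site practice may well differ, and a change of posture between visits could create or hide a change from baseline.

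For laboratory values, a marked and a trivial abnormality that are both labelled NCS fall in the same shift-table cell. Under Protocol 7, a laboratory abnormality becomes an AE only if it comes with signs and symptoms or needs intervention, so the AE tables need not show it either.

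**Working it through.** The plan states no figure to reproduce here. The check compares each set of limits with what is collected and analysed.

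**1. The promised count.** Protocol 9.6 and the synopsis promise it; Appendix 2 is the only numeric definition in the documents; SAP 8.3 and SAP 9.3 plan no such count; SAP 4.8 is silent. This is an undeclared departure.

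**2. Heart rate when posture is unknown.** Inputs are the Appendix 2 limits: supine below 35 or above 120, erect below 40 or above 140. For whole-number rates:

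| Heart rate (bpm) | Supine | Erect | Flag if posture unknown |
|---|---|---|---|
| below 35 | yes | yes | flagged |
| 35–39 | no | yes | undetermined |
| 40–120 | no | no | not flagged |
| 121–140 | yes | no | undetermined |
| above 140 | yes | yes | flagged |

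That is 5 + 20 = 25 undetermined values. A rate of 125 is flagged if supine and not if erect; 38 is the reverse. A semi-supine reading, the one posture that 6.4 names, has no limit of its own.

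**3. Blood pressure.** The rule is defined, but it holds only when both readings share a posture. Without recorded posture that condition cannot be checked.

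**4. QT correction.** With RR = 60/HR in seconds, Bazett is QT/RR^(1/2) and Fridericia (QTcF) is QT/RR^(1/3). For an illustrative QT of 385 ms at 90 bpm, RR = 0.667 s, giving:

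- Bazett: 385/0.667^(1/2) = 471.5 ms
- Fridericia: 385/0.667^(1/3) = 440.7 ms

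The Appendix 3 limit for men, and for women up to age 50, is above 470 ms, so the two corrections fall on opposite sides. Because QTcB = QTcF × (HR/60)^(1/6), the QTcF equivalent to each Bazett limit is:

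| HR (bpm) | Bazett 470 ms | Bazett 480 ms |
|---|---|---|
| 50 | 484.5 | 494.8 |
| 60 | 470.0 | 480.0 |
| 80 | 448.0 | 457.5 |
| 100 | 431.6 | 440.8 |

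At 100 bpm the 470 ms limit moves by 470 − 431.6 = 38.4 ms. The same identity lets Bazett QTc be recovered from QTcF and ECG heart rate, both of which SAP 8.4 lists.

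**5. QT and eligibility.** Protocol 6.5 evaluates QTc/QTcF for eligibility. None of the 11 inclusion or 22 exclusion criteria in Section 4 contains a QT limit.

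**6. Laboratory limits.** Appendix 2 has 21 laboratory and urine items. Nine are fixed values that apply directly to a recorded result: haemoglobin, haematocrit, platelets, creatinine, glucose, uric acid, calcium, and urine white and red cells. The other 12 need the local laboratory's reference limits. As an illustration, ALT at 2.5 × ULN exceeds the Appendix 2 limit of 2 × ULN and ALT at 1.05 × ULN does not. If both are labelled NCS, the shift table does not separate them.

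**7. Repeats and triplicates.** Neither document says which value is analysed when a reading is repeated, or how three ECGs are combined. The SAP 4.1 baseline table has no ECG row.

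**8. Scale.** With four patients per cohort, one patient changing category moves a cohort percentage by 1/4 = 25 points.

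**The case against.** A reader might infer that the limits in Appendices 2 and 3 cannot be applied to the data at all. The documents do not support that. All 21 laboratory and urine items can be applied, 12 of them once reference limits are available. Heart rates of 40–120 bpm are unaffected by posture, and Inclusion 2 requires vital signs within normal ranges at entry. Bazett QTc can be derived. Only the 24-hour ectopic-beat counts are out of reach, because no 24-hour recording is scheduled.

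A reader might also infer that laboratory data are judged only through the investigator's label. That is true of the categories, not of the data: SAP 8.2 summarises numeric values, SAP 4.1 includes minimum and maximum, and Listings 16.2.8.1 to 16.2.8.3 show the laboratory results. In a cohort of four, an extreme value is visible to anyone who looks.

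Nor do the documents show that the plan uses the wrong QT correction. The unnamed QTc may be Bazett; what is missing is its name. Clinically significant ECG findings after Screening are recorded as AEs under Protocol 6.5.

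Finally, Protocol 3.2 expects plasma levels close to or below the 10 ng/ml detection limit, post-dose laboratory tests and ECGs occur only at Day 28, and the primary endpoints are ophthalmic findings and AEs.

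All of this stands, and it lowers the priority. It does not explain the missing vital-signs count, the unspecified posture, or an eligibility sentence with no matching criterion.

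**Conclusion.** The point holds as a gap between the limits the protocol sets and the analysis the SAP plans. The vital-signs count is absent and its removal undeclared. Without recorded posture, the heart-rate flag is undetermined for 25 whole-number rates and the blood-pressure rule cannot be verified. The QT passages do not fit together: an eligibility reference without a limit, limits for one correction, and an unnamed QTc in the SAP. The only categorical laboratory analysis rests on an open-label label.

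This rests on two assumptions. The eCRF is not among the documents and might record posture, the QT correction or reference ranges; if it records posture, the posture part becomes a matter of stating which limits apply. The QT and ALT examples are illustrative, not trial data. Priority is minor to moderate. No view is taken on which clinical limit is right; the passages need to be reconciled.

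**What to change.** **(a) SAP 8.2 to 8.4.** Add one table, by cohort and overall, of patients with a vital sign, laboratory or ECG-interval value after injection that crosses an Appendix 2 or 3 limit not crossed at Baseline (vital signs) or Screening (laboratory, ECG). For blood pressure, count changes from baseline beyond the limit. Use the scheduled value, and for ECGs the mean of the triplicate; show repeats in the listings. Keep the investigator's label as supporting information. Leave out limits that need 24-hour recording. This restores the Protocol 9.6 count; if it is not restored, declare its removal in SAP 4.8.

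**(b) Protocol 6.4.** Use one consistent posture for scheduled readings, record it in the eCRF, and state which Appendix 2 limits apply to it. SAP 4.8 says the study closes at cohort 3, so this may come too late. If data collection is complete, show the heart-rate count under both the supine and the erect limits, and state that the same-posture condition for blood pressure could not be checked.

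**(c) QT.** Name the correction behind QTc in SAP 8.4, derive Bazett QTc where Appendix 3 needs it, and reconcile Protocol 6.5, Section 4 and Appendix 3.

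**Cost.** Wording changes, one eCRF field if still possible, and one extra table. Local reference limits must be in the database for 12 of the laboratory items. Some flagged values will be ones the investigator considers unimportant.

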6.5 Twelve-Lead Electrocardiogram

Triplet 12-lead electrocardiograms (ECGs) will be performed within a 5-minute interval at the time points outlined in Table 1.

The patient should be stabilized in a supine position for 5 minutes before recording the ECG at Screening. The ECG recordings should allow a full assessment of QT intervals. Machine-read values for QTc/QTcF will be evaluated for determination of eligibility at Screening. If the quality of the ECG is insufficient then it must be repeated. All ECG data must be reviewed by the attending physician and any findings of clinical significance found following Screening will be recorded as AEs in the eCRF. In addition, advice may be sought from appropriate cardiologists, if necessary. All ECGs will be made available to the Sponsor for review and might be sent to a Cardiac Core Laboratory for further evaluation.

6.6 Clinical Laboratory Tests

Safety laboratory tests will be performed at the time points specified in Table 1 and sent to a local laboratory. Additional tests may be performed at the discretion of the Investigator if deemed clinically appropriate. If required, samples may be sent to a central laboratory for confirmation of local results.

A full list of the clinical laboratory tests that will be performed and analyzed is presented in Section 21.1.

Any safety laboratory results outside the normal range will be repeated at the discretion of the Investigator and will be evaluated by the Investigator or designee as "clinically significant (CS)" or "not clinically significant (NCS)." Any CS value should be repeated as necessary and followed until resolution.

6.7 Ophthalmic Examination Procedures

Detailed ophthalmic examination will be used to evaluate screening criteria, determine efficacy and as a safety measure. All procedures should be performed at the times outlined in Table 1. The primary efficacy variable is vitreous haze. The ophthalmologist will grade vitreous haze by viewing the optic disc and posterior retina using an indirect ophthalmoscope set to large beam and mid power illumination with a 20-diopter lens. Low ambient lighting and the same indirect ophthalmoscope should be used whenever possible. The scale is based on the following unit scale categorized as follows:

| | |
|------|--|
| 0 | No inflammation |
| +0.5 | Trace inflammation (slight blurring of the optic disc margins and/or loss of the NFL reflex) |
| +1 | Mild blurring of retinal vessels and optic nerve |

| | |
|------|---|
| +1.5 | Optic nerve head and posterior retinal view obscuration greater than +1, but less than +2 |
| +2 | Moderate blurring of optic nerve head |
| +3 | Marked blurring of optic nerve head |
| +4 | Optic nerve head not visible |

6.7.1 Electroretinography

Patients will receive anaesthetic drops and the patient's eyelids will be kept open with a speculum. An electrode is gently placed on each eye and an additional electrode is placed on the skin to provide a ground. Electrical signals produced by the retina in response to light will be measured with the electrodes.

6.7.2 Fluorescein Angiogram

Fluorescein angiograms will be used to assess blood flow in the retina and choroid. Dilation eye drops will be given to patients, who will then place their chin on a chin rest and forehead against a support bar. Images of the retina, papilla, macular region and the choroid will be taken.

6.7.3 Optical Coherence Tomography

Three-dimensional images of the eye will be generated using optical coherence tomography (OCT). OCT is a laser-based, non-invasive, diagnostic system providing high-resolution images of the retina and retinal thickness. Optical coherence tomography will be performed in the study eye only. High-resolution cross-sectional images will be examined for physiological abnormalities.

6.7.4 Best Corrected Visual Acuity

Best corrected visual acuity will be measured in both eyes using an ETDRS chart. Patients will be asked to read the smallest letters they can from a chart.

6.7.5 Visual Field Measurement

Computerised 30° visual field measurement will be conducted.

6.7.6 Visually Evoked Cortical Potential

The electrical response of the primary visual cortex to a visual stimulus will be measured. Three electrodes will be placed on the scalp. One electrode will measure the response, another electrode will be placed at a reference location, typically on the forehead or top of the head. The third electrode will be placed on the patient's ear for grounding. These electrodes will be connected to a visual electrodiagnostic test system.

6.7.7 Intraocular Pressure

Intraocular pressure will be measured using Goldman contact tonometry.

6.7.8 Slit Lamp Examination

A slit lamp will be used to examine the conjunctiva, cornea, anterior chamber including grading of cells and haze (classified according to Standardization of Uveitis Nomenclature Working Group criteria), lens (classified according to Lens opacities classification system II) and vitreal haze (classified according to Standardization of Uveitis Nomenclature Working Group).

6.7.9 Dilated Fundoscopy

Visualization of the fundus will be carried out as part of an eye exam by dilating the patient's pupils. This procedure will include slit lamp biomicroscopy of the fundus.

6.7.10 Corneal endothelial microscopy

The corneal endothelial layer will be assessed by microscopic evaluation of the cornea.

6.7.11 Fundus photography

The eye, retina, retinal vasculature, optic disc, macula and posterior pole will be photographed using a retinal camera. Vitreous haze will also be documented.

6.7.12 Amsler grid

To test for macular degeneration, patients will be asked to look at an Amsler grid and wear their reading glasses. With one eye covered, patients will be asked to state if any of the lines appear wavy, blurred or distorted, whether there are missing or dark areas in the grid. The test will be repeated for both eyes.

6.7.13 Health Outcome Measures

Patient-reported outcomes will be assessed using the National Eye Institute Visual Functioning Questionnaire 25 (VFQ-25), SF36™ Health Survey Version 2 (SF-36v2) and EuroQol-5 Dimensions Health Questionnaire (EQ-5D). For additional information on these outcome measures, refer to the Procedure Manual.

6.8 Telephone Interview

A telephone interview will take place on Day 1 to evaluate the safety of PP-001. Standardized questions will be used and will include (but not be limited to) assessment of pain, blurred vision, change in visual acuity and eye redness.

6.9 Prior and Concomitant Medications

Prior and concomitant medications that will be recorded include prescription medications, dietary supplements/vitamins and over-the-counter medications. Topical medications will be recorded only if used as treatment for an AE. The minimum requirement is that drug name, indication and the start and stop dates of administration are to be recorded.

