9. Have been receiving an adequate therapy of e.g. systemic corticosteroid treatment or immunosuppressive therapy (e.g. azathioprine, methotrexate, cyclosporine, mycophenolate, tacrolimus) or any combination thereof. Any systemic therapy at study start should be continued throughout the study.
10. Best-corrected Early Treatment Diabetic Retinopathy Study (ETDRS) visual acuity of 10 letters or better (approximately 1/35 or 0.032) but equal or less than 50 letters (approximately 20/100 or 0.2) in the study eye.
11. Best-corrected ETDRS visual acuity of 50 letters or better in the fellow eye (approximately 20/100 or 0.2).

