6.9.1 Prior Medications

A medication history will be taken at Screening. All medications taken within 1 week before Day 0 will be entered into the eCRF.

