6.9.2 Concomitant Medication

All concomitant medications taken during the study will be recorded in the patient's eCRF.

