6.10 Prohibited Medications

The following medications are prohibited:

- Local biologicals
- Cyclophosphamide or chlorambucil
- Immunosuppressive, immunomodulatory or steroid treatment for any other disease than uveitis
- Any anticoagulant or thrombocyte aggregation inhibiting agent (marcumar, warfarin, heparin, enoxaparin, apixaban, rivaroxaban, pentosanpolysulfate, dabigatran, aspirin and others)
- Any systemic antibiotic treatment

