5.6 Prior and concomitant medications

Definitions and data conventions

The following categories of medications will be identified:

- previous medication (stop date \leq date of first study medication intake);
- concomitant medication (stop date $>$ date of first study medication intake or stop date ongoing/missing).

In case of missing or incomplete dates/times not directly allowing allocation to any of the two categories of medications, a worst-case allocation will be done according to the available parts of the start and the end dates. The medication will be allocated to the first category allowed by the available data, according to the following order:

- concomitant medication;
- previous medication.

Statistical analysis

Previous and Concomitant medications

Medications will be coded using WHO Drug Dictionary (WHO-DD), version 2016Q1 (1st Quarter of 2016), and the following Anatomical Therapeutic Chemical Classification (ATC) codes:

- Anatomical Main Group (ATC 1st level code);
- Chemical subgroup (ATC 4th level code);
- Preferred name.

Previous and concomitant medications will be summarized separately for Safety set by anatomical main group, chemical subgroup and preferred name by cohort.

Subjects experiencing more than one previous (or concomitant) medication within the same anatomical main group, chemical subgroup and preferred name will be counted only once.

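### SAP 5.6 tabulates a treatment given after the injection as 'previous' if it also ends on Day 0, and Protocol 6.9 does not require the dose of systemic uveitis therapy to be recorded

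*Protocol*

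**What the plan says.** **Recording.** Protocol 6.9 sets the minimum medication record: "The minimum requirement is that drug name, indication and the start and stop dates of administration are to be recorded". Neither dose, nor route, nor clock time is on that list. Protocol 6.9.2 adds: "All concomitant medications taken during the study will be recorded in the patient's eCRF".

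**Background therapy.** Inclusion criterion 9 (Protocol 4.1) says: "Any systemic therapy at study start should be continued throughout the study". It does not ask for a stable dose. Protocol 1.1 describes high-dose corticosteroids being tapered slowly as disease activity allows.

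**Classification.** SAP 5.6 defines the first category as "previous medication (stop date \leq date of first study medication intake"), where the operator means on or before. A medication is concomitant if its stop date is later than the "date of first study medication intake or stop date ongoing/missing". SAP 5.3 fixes the date of first intake as the date of the Day 0 injection. Where missing or incomplete dates or times prevent allocation, SAP 5.6 tries concomitant first. The two categories go to Tables 14.1.6.1 and 14.1.6.2, and all medications to Listing 16.2.4.3.

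**Adverse events.** SAP 8.1 defines a treatment-emergent event by the date and time of its onset relative to the injection.

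**Efficacy.** SAP 7.1 summarises best corrected visual acuity (BCVA) and its change from baseline by visit and cohort, with Days 14 and 28 as the primary efficacy time points. Vitreous haze is secondary (SAP 3.5.2). SAP 4.3 and 4.4 foresee no subgroups or covariates.

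**The concern.** The main purpose of this first-in-human study is safety. Protocol 6.1 keeps patients in hospital for at least 4 hours after injection because an acute loss of vision or an acute inflammatory or toxic response is thought possible. Treatment of such a reaction is among the most informative medication records the trial can produce. If it is given once and ends the same day, SAP 5.6 puts it in the table of medications that preceded the study drug. A reader of the safety tables would see a treatment-emergent event with no matching treatment among the concomitant medications.

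The second issue concerns how efficacy is read. With no control arm and four patients per cohort, a change in BCVA or vitreous haze can be interpreted only alongside what else was being given for the uveitis. A systemic drug that is continued at a higher or lower dose satisfies inclusion criterion 9 and the minimum record in Protocol 6.9. The change therefore need leave no required trace.

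**Working it through.** The plan gives no figure to reproduce on this point: SAP 3.3 states no power calculation, and no effect size or standard deviation is given. The check has three parts.

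**1. Apply the SAP 5.6 rule to constructed records.** The rule as written makes a medication concomitant if its stop date is after the injection date, ongoing or missing, and previous otherwise. The alternative uses date and time, as SAP 8.1 does for events: concomitant if the stop date/time is at or after the injection, ongoing or missing, and previous otherwise.

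| Record | SAP 5.6 | Date/time rule |
|---|---|---|
| Systemic therapy, ongoing | concomitant | concomitant |
| Systemic therapy, stopped Day 14 | concomitant | concomitant |
| One-off, Day 0, 4 h after injection | **previous** | **concomitant** |
| One-off, Day 0, 1 h before injection | previous | previous |
| Course begun Day 0 after injection, stopped Day 5 | concomitant | concomitant |
| One-off, Day 1 | concomitant | concomitant |
| Long-term drug, last dose Day 0 after injection | **previous** | **concomitant** |

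Two of the seven change class, and both have a stop date of Day 0. The records are examples chosen to test the rule, so 2 of 7 is not an expected frequency.

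**2. See whether another provision catches these records.** The concomitant-first fallback in SAP 5.6 applies only when missing or incomplete dates or times prevent allocation. A stop date of Day 0 is complete and allocates directly to 'previous', so the fallback is not triggered. Listing 16.2.4.3 still shows the record. Protocol 5.7 requires the clock time of the injection, but Protocol 6.9 does not require one for other medications, so the listing may not show which came first.

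**3. Size of an unseen dose change.** Let m patients in a cohort of n each have BCVA moved by d letters by other therapy. The cohort mean then moves by m × d / n. The cohort size n = 4 comes from SAP 3.1; n = 6 applies if two patients are added at a lower dose (4 + 2). The documents give no value for d, so 5, 10 and 15 letters are assumptions.

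- n = 4, m = 1: 5/4 = 1.25; 10/4 = 2.5; 15/4 = 3.75 letters.
- n = 4, m = 2: 10/4 = 2.5; 20/4 = 5.0; 30/4 = 7.5 letters.
- n = 6, m = 1: 5/6 = 0.83; 10/6 = 1.67; 15/6 = 2.5 letters.

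**The case against.** The strongest reply is that most co-treatment is visible, and this is right. A systemic or injected therapy added after Day 0 must be recorded with its name, indication and start date, and it appears in the listing. A reader might infer that uveitis co-treatment cannot be traced at all; the documents do not support that. The recording gap is limited to dose changes within an existing record.

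A reader might also infer that everything given after the injection on Day 0 is called 'previous'. It is not: a course that runs to Day 1 or later, or has an ongoing or missing stop date, is concomitant. Continuing background therapy is classed correctly.

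The list in Protocol 6.9 is a stated minimum. The eCRF and the table and listing shells are not among the documents, so dose and clock time may be collected. This stands, and it makes the second part of the point conditional.

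Protocol 6.9.1 says: "All medications taken within 1 week before Day 0 will be entered into the eCRF". It is tempting to conclude that a steroid stopped on Day -8 goes unrecorded. But Table 1 collects concomitant medication from Screening, which may be as early as Day -14, so such a drug may be captured. It could be missed if Screening falls in the last week.

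Protocol 6.10 prohibits "Immunosuppressive, immunomodulatory or steroid treatment for any other disease than uveitis", which might suggest that new uveitis therapy after Day 0 can never be a deviation. The documents do not say so, and SAP 5.2 has violations judged case by case.

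Finally, efficacy is secondary and descriptive, and without a control arm BCVA change could not be attributed firmly to PP-001 even with complete dose records. That limits the consequence. It does not remove the need to see dose changes when reading four individual patients.

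**Conclusion.** The point holds in two limited parts.

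The SAP 5.6 boundary is wrong as written. Any medication given after the injection that also ends on Day 0 is tabulated as pre-study, and this disagrees with the date/time rule in SAP 8.1. It affects the label and the summary table; the record itself is kept. How many records are affected cannot be known from the documents.

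The minimum medication record omits dose and dose-change dates for systemic uveitis therapy, so a dose change during the study need not be visible beside BCVA and vitreous haze. This assumes that the eCRF collects no more than the protocol requires, which the documents do not settle. The effect of one affected patient in a cohort of four, 1.25 to 3.75 letters, rests on an assumed individual change of 5 to 15 letters and shows leverage only. Nothing in the documents shows that such a change occurred, or that an effect of other therapy was credited to PP-001.

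Topical treatment is outside this point. Protocol 6.9 says "Topical medications will be recorded only if used as treatment for an AE", which does not agree with the wider wording of Protocol 6.9.2, and the two should be reconciled separately.

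**What to change.** **SAP 5.6.** Define 'previous' as stopped before the date and time of injection. Assign Day 0 medications by time, or to concomitant when time is missing or not collected. In Table 14.1.6.2, show medications started on or after injection as a separate block.

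**Protocol 6.9.** For systemic and injected uveitis therapy, require dose, route and the date of each dose change. List these changes beside each patient's BCVA and vitreous haze. If the eCRF already holds these fields, only the listing is needed. If it does not, the hospital notes or source forms named in Protocol 15.1 are the place to look.

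**Cost.** A short change to SAP 5.6, one table block, one listing and a few more eCRF entries. Some Day 0 medications given before the injection, but without a recorded time, would move to concomitant. That follows the order SAP 5.6 already uses when dates or times are incomplete. No change to permitted treatment is proposed.
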